IV	Intravenous
Kg	Kilogram
L	Liter
LDH	Lactic dehydrogenase
MedDRA	Medical dictionary for regulatory activities
mg	Milligram
mL	Milliliter
N	Number
NCI	National Cancer Institute
PCS	Potentially clinically significant
SAP	Statistical Analysis Plan
SOC	System organ class
U.S.	United States
vs.	Versus
w/v	weight / volume

1. INTRODUCTION

Ferric Carboxymaltose (FCM) is a parenteral form of iron that can be used to treat iron deficiency (IDA) when oral iron is either ineffective or contraindicated [Lyseng-Williamson, 2009]. Several randomized controlled trials demonstrated the efficacy and safety of intravenous (IV) FCM for treating iron deficiency associated with chronic kidney disease, inflammatory bowel disease, heavy uterine bleeding, and during the postpartum period [Barish, 2012; Breymann, 2008; Evstatiev, 2011; Kulnigg, 2008; Qunibi, 2011; Seid, 2008; Van Wyck, 2007; Van Wyck, 2009; Charytan, 2012]. In these populations, several patients who received FCM developed transient and asymptomatic reductions in serum phosphate that typically appeared within 2 to 4 weeks of treatment and resolved spontaneously within 6 to 12 weeks [Van Wyck, 2009].

1.1. Pathophysiology

Phosphate is the most abundant intracellular anion and is essential for membrane structure, energy storage, and transport in all cells. Approximately 85% of the body's phosphorus is in bone as hydroxyapatite, while most of the remainder (15%) is present in soft tissue. Only 0.1 % of phosphorus is present in extracellular fluid and it is this fraction that is measured with a serum phosphorus level [Moe, 2008]. Phosphorus homeostasis is complex and is regulated by several hormones. Hypophosphatemia can occur in the presence of low, normal, or high total body phosphate. In the latter two instances, a shift from the extracellular pool into the intracellular compartment is a major contributory factor. Parathyroid hormone causes phosphate to be released from bone and inhibits renal reabsorption of phosphate, resulting in phosphaturia. Vitamin D aids in the intestinal absorption of phosphate. Thyroid hormone and growth hormone act to increase renal reabsorption of phosphate. Finally, a new class of phosphate-regulating factors, the so-called phosphatonins, including fibroblast growth factor 23 (FGF23), have been shown to be important in phosphate-wasting diseases, such as oncogenic osteomalacia, X-linked and autosomal dominant hypophosphatemic rickets, autosomal recessive hypophosphatemia, and tumoral calcinosis [Shaikh, 2008]. Additionally, FGF23 is up-regulated in patients with early-stage chronic kidney disease to prevent hyperphosphatemia [Takeda, 2011]. A link between IV iron application and increase in FGF23 has been proposed [Takeda, 2011; Schouten, 2009a].

Serum phosphorus concentration is determined by several factors. Dietary phosphorus intake, stage of growth and time of day contribute to the variability of fasting serum phosphorus concentrations. Optimal cellular function is dependent on maintenance of a normal serum phosphorus concentration. The most important determinant of serum phosphorus concentration is regulation of phosphorus reabsorption by the kidney. The majority of this reabsorption (80%) occurs in the proximal tubule and is mediated by an isoform of the Na-phosphate-cotransporter. Parathyroid hormone, via a variety of intracellular signaling cascades leads to Na-phosphate-IIa internalization and down-regulation, and is the main regulator of renal phosphate reabsorption.

Hypophosphatemia is observed in approximately 2% of hospitalized patients, and can be related to decreased intestinal absorption of phosphorus, re-distribution of phosphorus from the extracellular to the intracellular compartment, increased loss of phosphorus through the kidneys, or any combination of these processes. The most common manifestation of hypophosphatemia in hospitalized patients is secondary to re-distribution of phosphorus as a result of respiratory

alkalosis [Amanzadeh, 2006]. Hypophosphatemia has been implicated as a cause of rhabdomyolysis, respiratory failure, hemolysis and left ventricular dysfunction. With the exception of ventilated patients, there is little evidence that moderate hypophosphatemia has significant clinical consequences in humans, and aggressive IV phosphate replacement is unnecessary.

The data on the incidence of hypophosphatemia (defined as <0.64 mmol/L) in outpatients is sparse, but has been reported as 0.9% [Betro, 1972].

1.2. Increased FGF23

Studies have shown that IV FCM, iron polymaltose and saccharated ferric oxide increase the levels of FGF23 post-infusion [Takeda, 2001; Schouten, 2009b; Wolf, 2013]. This hormone, besides the parathyroid hormone, is key for serum phosphate regulation. The phosphatonin FGF23 has been shown to decrease serum phosphate levels by reducing the number of Na-phosphate-cotransporters in the proximal tubule and by inhibiting the production of the active form of Vitamin D [Razzaque, 2007]. FGF23 is predominantly expressed in bone osteocytes [Liu, 2006]. Increased concentrations of circulating FGF23 are central to the pathogenesis of several hypophosphatemic diseases including autosomal-dominant, -recessive, and X-linked hypophosphatemic rickets, tumor-induced osteomalacia and selected cases of McCune-Albright syndrome [Imel, 2005; Yamamoto, 2005].

A study tested the association of IDA with cFGF23 (the C-terminal form of the protein) and iFGF23 (only the intact and hence active form) levels in 55 women with a history of heavy uterine bleeding, and assessed the longitudinal biochemical response over 35 days to equivalent doses of randomly assigned, IV elemental iron in the form of FCM or iron dextran [Wolf, 2013]. The IDA was associated with markedly elevated cFGF23 (807.8 ± 123.9 RU/mL) but normal iFGF23 (28.5 ± 1.1 pg/mL) levels at baseline. Within 24 hours of iron administration, cFGF23 levels decreased by approximately 80% in both groups. In contrast, iFGF23 transiently increased in the FCM group alone, and was followed by a transient, asymptomatic reduction in serum phosphate <2.0 mg P/dL in 10 women in the FCM group compared to none in the iron dextran group. Reduced serum phosphate was accompanied by increased urinary fractional excretion of phosphate, decreased calcitriol levels and increased parathyroid hormone levels. These findings suggest the IDA increases cFGF23 levels, and that certain iron preparations temporarily increase iFGF23 levels. It may therefore be concluded that IV iron lowers cFGF23 in humans by reducing FGF23 transcription as it does in mice, whereas carbohydrate moieties in certain iron preparations may simultaneously inhibit FGF23 degradation in osteocytes leading to transient increases in iFGF23 and reduced serum phosphate. Overall, it seems plausible that an increase in iFGF23 with all the downstream effects may be induced by application of IV iron.

1.3. Inhibition of Vitamin D Activation

It has been described that IV iron might have an inhibitory effect on renal 25-(OH)-Vitamin D 1α -hydroxylase expression [Sato, 1997]. This in turn reduces the availability of 1,25-(OH) $_2$ -Vitamin D $_3$, which leads to decreased absorption of phosphate from the gut and to decreased reabsorption of filtered phosphate in the proximal tubules of the kidney [Sato, 1997]. However, this mechanism was proposed before FGF23 was found to be a direct inhibitor of 1α -hydroxylase expression and it can be assumed that the effect of IV iron on 1α -hydroxylase expression is

triggered via an increase in FGF23 concentration (as mentioned above), which leads to decreased production and increased degradation of 25-(OH)-Vitamin D 1 α -hydroxylase [Shimada, 2011; Shimada, 2004a; Shimada, 2004b].

1.4. Symptoms and Signs of Hypophosphatemia

Although an FGF23-mediated decrease in serum phosphate after a single infusion of iron is usually transient, the risk of developing clinical symptoms and the actual clinical presentation is determined by the severity of hypophosphatemia and the time to recovery. Management of hypophosphatemia is within the judgment and discretion of the investigator.

Patients with hypophosphatemia typically report bone pain, general weakness, and asthenia [Okada, 1982; Schouten, 2009b; Mani, 2010; Shiraki, 1986; Sato, 1998; Suzuki, 1998; Konjiki, 1994; Shimizu, 2009; Yamamoto, 2013; Moore, 2013; Blazevic, 2014; Fierz, 2014; Vandemergel, 2014; Barea Mendoza, 2014; Poursac, 2015; Sangros Sahun, 2016]. In severe cases, proximal myopathy that also affects the diaphragm and rhabdomyolysis have been reported. The latter can also affect the heart or cause cardiomyopathy or cardiac arrhythmias [Bacchetta, 2012]. Rare manifestations include hemolysis, encephalopathy, seizures [Haglin, 2016]. The type of clinical manifestation expression is also dependent on the age at onset and the duration of hypophosphatemia. Young patients with long-standing hypophosphatemia typically present with growth retardation, delayed dentation and rickets [Elder, 2014]. In adults with hypophosphatemia persisting for several months, long-term complications such as osteomalacia can occur (Fig.2) [Gonciulea, 2017]. Presentation of osteomalacia can include bone pain, fractures, and pseudofractures, which may be difficult to diagnose on conventional X-ray.

Radiological findings are a coarse trabecular structure, and a loss of secondary trabeculae [Phan, 2016]. Low trauma fractures affecting the ribs or scapular “stress-“ fractures of the lumbar spine, pelvic structures, and long bones such as femur, tibia, or metatarsal are also common complications of osteomalacia. More sensitive diagnostic tests to identify looser zones, known as 'pseudofractures,' include computed tomography, magnetic resonance imaging, and bone scintigraphy. Bone biopsy showing increased ratio of osteoid to bone surface and reduced tetracycline labeling remains the gold standard for diagnosis, but is rarely performed due to its invasiveness. Although there is no specific laboratory test for osteomalacia, mildly elevated total and bone-specific alkaline phosphatase in plasma have been repeatedly reported in the context of iron-induced hypophosphatemia [Phan, 2016].

2. SUB-STUDY OBJECTIVE

The objective of this sub-study is to characterize serum phosphorus levels over time in participants with heart failure with iron deficiency after dosing with FCM versus placebo.

3. SUB-STUDY RATIONALE AND DESIGN

3.1. Sub-Study Rationale

In two randomized clinical studies conducted with FCM (1VIT09030 and 1VIT09031), hypophosphatemia was an adverse drug reaction (treatment emergent adverse event assessed as

related by the Investigator) that occurred in 2.1% (37/1775) of the study participants. Transient decreases in laboratory blood phosphorus levels (< 2 mg/dL) were observed in 27% (440/1638) of participants. Mean decreases from baseline in phosphorus occurred by Day 7, were highest at Day 14 and were returning toward baseline at Day 35 (1VIT09031) or Day 56 (1VIT09030). The objective of this sub-study is to characterize serum phosphorus levels over time in participants with heart failure with iron deficiency after dosing with FCM versus placebo.

3.2. Sub-Study Design

Participation in the sub-study is optional. Although all investigational sites are encouraged to participate, each study site's participation will be determined based on the feasibility of the site to participate. If a site decides to participate, all subsequent participants at the sites will be invited to enroll in the sub-study until enrollment of 110 study participants is achieved. Sites and participants have the option to perform sub-study visits either at the clinic or at a home visit.

A total of approximately 110 participants will be enrolled and the sample size has been determined based on the feasibility of enrollment. Sub-study duration will be up to 6 months for each participant. With this number of participants to be enrolled in the sub-study and the current knowledge on the course of hypophosphatemia with FCM, the evaluation after the initial dosing regimen only was determined to be sufficient to characterize the course of hypophosphatemia in participants with congestive heart failure. A separate informed consent form (ICF) for the sub-study will be signed by participants. Each participant in the sub-study will have additional blood samples collected at either clinic visits or at home visits on Days 14 ± 3 , 21 ± 3 , 35 ± 3 , 63 ± 3 , 91 ± 3 , and 119 ± 3 . These samples are in addition to the baseline (Day 0) and 6 month (Day 160-176) blood samples collected at the clinic visits for the main study.

3.3. Schedule of Events for Sub-Study

Table 1. Schedule of Events for Sub-Study

Visit Week of main-study	Screening	Treatment Phase		Follow-up Phase							
	-28 to -1	Day 0	Day 7±2 1	Day 14±3* 2	Day 21±3* 3	Day 35±3* 5	Day 63±3* 9	Day 90±14† 13	Day 91±3* 13	Day 119±3* 17	Day 160-176, Day 180, Day 187, EOS
	Participant follows the main study schedule of events							Participant follows the main study			Participant follows the main study schedule of events
Check that informed consent was signed at screening or at Day 0				X							
Inclusion/ Exclusion criteria				X							
Complete study activities as outlined in the main study Section 3.3	X							X			X
Serum Chemistry (see Section 6.5)				X	X	X	X		X	X	
1,25 (OH) ₂ Vitamin D‡				X	X	X	X		X	X	
25 (OH) Vitamin D‡				X	X	X	X		X	X	
Parathyroid Hormone‡				X	X	X	X		X	X	

* In Clinic or Home visit

† Phone call or clinic visit

‡ Reminder that laboratory testing for 1,25 (OH)₂ Vitamin D, 25 (OH)₂ Vitamin D, and Parathyroid Hormone levels are also done outside the hypophosphatemia substudy at Day 0 and Day 160-176

4. PARTICIPANT SELECTION

4.1. Number and Type of Participants

Approximately 110 participants newly enrolled in the main 1VIT15043 study, who fulfill the inclusion criteria, do not meet any of the exclusion criteria and who have given written informed consent will be included.

4.2. Participant Selection

4.2.1. Inclusion Criteria

1. Demonstrate the ability to understand the requirements of the sub-study, willingness to abide by sub-study participation, and to return for the required assessments.

4.2.2. Exclusion Criteria

1. History of primary hypophosphatemic disorder (for example X-linked hypophosphatemia)
2. Baseline serum phosphate <2.5 mg/dL
3. Untreated primary hyperparathyroidism.

4.3. Participant Assignment and Randomization Process

Please follow guidance as detailed in the main body of the protocol.

4.4. Withdrawal from Study

Please follow guidance as detailed in the main body of the protocol.

5. CONCOMITANT MEDICATION

Please follow guidance as detailed in the main body of the protocol.

6. STUDY PROCEDURES

6.1. Treatment Phase

For Day 0 and Day 7 visits, follow guidance as detailed in the main body of the protocol.

6.2. Informed Consent

Check that the participant signed an informed consent form for the hypophosphatemia study at screening or at Day 0.

Prior to any study specific procedures, the investigator or his or her designee must explain to each participant the nature of the study, study purpose, procedures to be performed, expected duration, and the benefits and risks of study participation. After this explanation the participant must voluntarily sign an informed consent statement (Required Elements of Informed Consent, 21 CFR 50.25). The participant will be given a copy of the signed consent form.

6.3. Follow-up Phase

Clinic visits will be performed by study personnel.

Home visits will be performed by a contracted third party person qualified to collect blood or site personnel.

Once a home visit or clinic visit choice has been made, that patient must continue with that venue for the those visits for the duration of their sub-study participation.

After completing the 6-month sub-study, the participant returns to follow the main study protocol.

6.3.1. Sub-study Specific Visit Days 14 ± 3 , 21 ± 3 , 35 ± 3 , 63 ± 3 , 91 ± 3 , 119 ± 3 (Clinic or Home Visits)

- Laboratory samples will be collected
 - Serum for:
 - Chemistry (see [Section 6.5](#) for details)
 - 1,25 (OH)₂ Vitamin D
 - 25 (OH) Vitamin D
 - Plasma for:
 - Parathyroid Hormone

Note that Visit Day 90 ± 14 days (Phone call or Study visit) is a procedure in the main protocol to collect adverse event / serious adverse event assessment, including evaluation of potential endpoint events (blinded staff).

Study Visit Day 91 ± 3 days will be an in-clinic visit (if the patient has chosen in-clinic visits) or a home visit (if the patient has chosen home visits) which will be performed by a qualified person to collect laboratory samples.

6.4. End of Sub-Study

Sub-study visits only occur within the first 180 days. No other sub-study dosing or blood collections will occur after that time.

6.5. Central Laboratory Assessment

Serum and plasma samples for laboratory analyses will be obtained at 1) Day 0 of the main study; 2) Days 14, 21, 35, 63, 91, and 119 at additional clinic visits or scheduled as home visits; 3) Day 160-178 of the main study. All serum and plasma laboratory testing shall be provided to the study personnel for review and assessment. The laboratory assessments will be determined as follows:

Chemistry: Sodium, potassium, chloride, BUN, creatinine, albumin, alkaline phosphatase, total bilirubin, GGT, AST, ALT, LDH, calcium, phosphate, glucose, bicarbonate and magnesium

Other: 1,25 dihydroxy Vitamin D; 25 hydroxy Vitamin D

Plasma: Parathyroid Hormone

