- i. All participants randomized will be dosed every 6 months. Participants randomized to the FCM arm will be dosed as indicated based on blood counts (i.e. Hgb <13.5 g/dL [females] or <15.0 g/dL [males])) and iron studies (i.e. serum ferritin <100 ng/mL or 100 to 300 ng/mL with TSAT <20%). Participants not meeting pre-specified laboratory criteria for blood counts and iron studies and all participants randomized to the placebo arm will be administered IV placebo infusion at each visit. The second of the 2 dosing visits should occur at Day 7±2 after the first dose.
- j. Prior to randomization
- k. Only for participants at select sites performing additional chemistry labs (1,25 (OH)₂ Vitamin D, 25 (OH) Vitamin D and PTH) (sub-study).
- l. May be performed via telephone or in person.
- m. Performed at Day 180 and Day 360 visits only.
- n. To be performed by unblinded site personnel. All other procedures must be performed by personnel blinded to the treatment assignment
- p. Hemoglobin only

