5.6 Blinding

All participants and blinded study staff will be blinded to the content of study drug for the duration of the trial.

During the period of study drug administration, the blinded personnel will not be with the subject or in a location that could result in the blind being inadvertently broken. However, the Principal Investigator or designee will be available in the event of an emergency, and/or the need for adverse event assessment. All blinded study personnel will be blinded to the post-treatment iron indices and serum phosphorous laboratory results, as the values may break the blind.

The blinding will be maintained until the study is complete, and the database has been locked. In the event of an emergency that would require the investigator to be aware of the treatment allocation prior to database lock, the investigator can obtain this information, on a per participant basis. **It is recommended to contact the sponsor's Medical Monitor or designee prior to unblinding.** If a participant's treatment assignment is unblinded, the sponsor must be contacted immediately via telephone.

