6.6 Laboratory Assessments

Serum samples for laboratory analyses must be obtained at all appropriate visits. The method of analysis of screening laboratory values will be by a central clinical laboratory. All visit laboratory samples will be analyzed by a central clinical laboratory. All laboratory testing will be provided to the investigator or his/her

medically qualified designee for review and assessment. Post dose iron indices and serum phosphorus results will be provided to the designated unblinded investigator for assessment. The laboratory assessments will be determined as listed in Section 3.3:

- Hematology: Hgb, Hct, RBC, WBC, MCV, MCH, MCHC, RDW, platelets, differential count, and reticulocyte count
- Chemistry: Sodium, potassium, chloride, BUN, creatinine, albumin, alkaline phosphatase, total bilirubin, GGT, AST, ALT, LDH, calcium, phosphorus, glucose, bicarbonate, and magnesium
- Iron indices: Serum iron, serum ferritin, total iron binding capacity (TIBC), and percentage serum transferrin saturation (TSAT)
- Other: 1,25 (OH)₂ Vitamin D, 25 (OH) Vitamin D and PTH, and NT-proBNP

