Appendix 1, Section 6.3.1, Sub-Study Specific Visit Days 14 ± 3, 21 ± 3, 35 ± 3, 63 ± 3, 91 ± 3, 119 ± 3 (Clinic or Home Visits)	Study Visit Day 91±3 days may will be an in-clinic visit (if the patient has chosen in-clinic visits) or is a home visit (if the patient has chosen home visits) which will be performed by a licensed qualified person to collect laboratory samples.

Appendix 1, Section 6.5 Central Laboratory Assessment
	
Serum and plasma Plasma samples for laboratory analyses will be obtained at 1) Day 0 of the main study; 2) Days 14, 21, 35, 63, 91, and 119 at additional clinic visits or scheduled as home visits; 3) At Day 160-178 of the main study. All serum and plasma laboratory testing shall will be provided to the unblinded study personnel for review and assessment. Investigators may refer to Appendix 1 for guidance in managing hypophosphatemia. The laboratory assessments will be determined as follows:

Appendix 1, Section 7.2 Reporting of Adverse Events
	
Please follow guidance for reporting of adverse events as detailed in the main body of the 1VIT15043 study protocol. For qualifying adverse events of hypophosphatemia, the National Cancer Institute (NCI) Common Terminology Criteria for Adverse Event (CTCAE Version 5.0) should be followed.
 
The serum phosphorus level normally ranges from 2.5-4.5 mg/dL or 0.80-1.45 mmol/L in adults. The reporting of hypophosphatemia, per the 2009 NCI CTCAE Version 4.0, is:
 
 • Grade 1: mild (<LLN-2.5 mg/dL; <LLN-0.8 mmol/L), • Grade 2: moderate (<2.5-2.0 mg/dL; <0.8-0.6 mmol/L), • Grade 3: severe (<2.0-1.0 mg/dL; <0.6-0.3 mmol/L), • Grade 4: potentially life threatening (< 1.0 mg/dL; <0.3 mmol/L; life-threatening consequences), • Grade 5: death. (NCI 2009 [NIH, 2009]). 
The updated 2017 NCI CTCAE Version 5.0 includes the revised categorization and reporting of hypophosphatemia to the following:

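### The hypophosphatemia sub-study's laboratory section omits the unblinded-only restriction that the main protocol places on post-dose phosphorus

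*Combined protocol and SAP*

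**What the plan says.** **Sub-study.** Appendix 1, section 6.5, in both copies of the appendix, states: "All serum and plasma laboratory testing shall be provided to the study personnel for review and assessment". The chemistry panel in that section includes phosphate ("LDH, calcium, phosphate, glucose"). Apart from Day 0 and a six-month main-study sample, the draws are on "Days 14, 21, 35, 63, 91, and 119 at additional clinic visits or scheduled as home visits". All of these follow the Day 0 and Day 7 doses.

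**Main protocol.** Section 5.6: "All blinded study personnel will be blinded to the post-treatment iron indices and serum phosphorous laboratory results, as the values may break the blind". Section 6.6 first sends all laboratory testing to the investigator or a medically qualified designee, then makes an exception: "Post dose iron indices and serum phosphorus results will be provided to the designated unblinded investigator for assessment".

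**Who is blinded.** Footnote n to the schedule in section 3.3, attached to randomization and study drug administration, reads: "To be performed by unblinded site personnel. All other procedures must be performed by personnel blinded to the treatment assignment". Section 6.4.3.1 assigns the 6MWT and the evaluation of potential endpoint events to blinded staff.

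**The concern.** The main protocol treats post-dose phosphorus as a marker of treatment and controls who sees it. The sub-study measures phosphorus more often than any other part of the trial, and its laboratory section has no such control.

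The staff who could see the values matter. The 6MWT depends on effort and encouragement. Its six-month change is the third tier of the primary endpoint (SAP v1.3, 5.1), and its twelve-month change is a secondary outcome (SAP v1.3, 5.5). Blinded site staff also decide which events to put forward as suspected endpoints. A tester or event reporter who believes that a participant is on FCM may behave differently, even without meaning to. All six sub-study draws come before both walks.

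**Working it through.** The point rests on a comparison of texts. The arithmetic afterwards only sizes it.

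**1. Is there a benign reading of section 6.5?**
- *Does the term mean unblinded staff?* No. Appendix 1, section 6.3 uses it for whoever runs the visits: "Clinic visits will be performed by study personnel". Under footnote n, only randomization and dosing fall to unblinded personnel.
- *Does Appendix 1 import the main routing rule?* Its pointers to the main body cover randomization, withdrawal, concomitant medication, the Day 0 and Day 7 visits, and adverse events. None covers who receives laboratory results.
- *How does 6.5 differ from main section 6.6?* Section 6.6 has a general release followed by an exception for iron indices and phosphorus. Section 6.5 has only the general release.
- *Do the rules meet on the same sample?* Yes. The six-month sample listed in 6.5 is a main-study sample, so its phosphorus falls under both 6.5 and 6.6.

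The two sections therefore give different recipients for the same analyte.

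**2. How many participants?**
- Sub-study size: about 110, or 55 per group (Appendix 1, 8.2). Trial size: about 3,014 (main protocol, 4.1). Share: 110 / 3,014 = 3.6%.
- Phosphorus below 2 mg/dL in two earlier FCM studies (Appendix 1, 3.1): 440 / 1,638 = 26.9%, which reproduces the stated 27%.
- If that rate carried over: 55 × 0.269 = 14.8, or about 15 FCM participants. As a share of the trial: 14.8 / 3,014 = 0.5%.

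**3. How revealing would such a value be?** With 1:1 allocation, the probability of FCM given a value below 2 mg/dL is p / (p + q), where p = 0.269 and q is the placebo rate. The documents give no q for this population, so a range is shown.

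| Placebo rate q | Source | Expected of 55 on placebo | Ratio p/q | Probability of FCM |
|---|---|---|---|---|
| 0.9% | outpatients, below 0.64 mmol/L (Appendix 1, 1.1) | 0.5 | 30 | 97% |
| 2% | hospitalized patients (Appendix 1, 1.1) | 1.1 | 13 | 93% |
| 5% | assumed | 2.8 | 5 | 84% |

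The outpatient cut-off of 0.64 mmol/L is about 1.98 mg/dL, close enough to 2 mg/dL for this purpose. Across the range, one low value points strongly to FCM.

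**4. Vitamin D and PTH.** Sections 5.6 and 6.6 do not mention them. Appendix 1, section 1.2 describes a study in which the fall in phosphate after FCM came with lower calcitriol (1,25(OH)2 vitamin D) and higher PTH. Masking phosphate alone would leave correlated signals visible.

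**The case against.** The strongest reply is that section 5.6 is unqualified, Appendix 1 belongs to the same protocol, and nothing exempts the sub-study. A site that applies 5.6 everywhere would withhold the phosphate from blinded staff whatever 6.5 says. Section 6.5 does not name blinded staff as recipients. This stands. A reader might infer that the sub-study tells sites to unblind themselves, but the documents support only that a restriction is missing where the results are released.

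A reader might also infer that the restriction was deliberately removed, because the version 3 entry in the amendment history reads: "All serum and plasma laboratory testing shall will be provided to the unblinded study personnel for review and assessment". The marks that distinguish deleted from added words do not survive in the text available, and the log describes superseded wording. It is context, not evidence of intent.

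The size is modest. The 27% comes from other populations, and section 3.1 does not say whether all 1,638 participants received FCM. The sub-study excludes baseline phosphate below 2.5 mg/dL, so the rate may differ here. A committee blinded to treatment adjudicates events (main protocol, 10.2). All of this stands, but adjudication protects neither the walk test nor the site's decision to report an event.

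Finally, sending everything in 6.5 to the unblinded investigator would go too far. It would move potassium, creatinine, liver enzymes and glucose away from the investigator or designee who receives them under 6.6 and judges laboratory abnormalities under 7.1. The fix must be limited to the revealing analytes.

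**Conclusion.** The inconsistency is real and lies in current text. Section 6.5 of Appendix 1 lacks the unblinded-only restriction that sections 5.6 and 6.6 attach to post-treatment phosphorus, and no other part of the appendix supplies it. Read alone, it permits blinded staff to see values that the protocol itself says may break the blind.

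The weakness touches about 3.6% of participants. About 15 on FCM, or 0.5% of the trial, would have a clearly low value if the earlier rate carries over, which is an assumption. The 84% to 97% probabilities also depend on placebo rates that are borrowed or assumed.

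A reader might infer that the primary result is at risk. The documents do not support that: the numbers are small, and no effect of unblinding on the 6MWT is given from which a bias could be estimated. The point is worth correcting because the gap is plain and closing it costs little.

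**What to change.** 1. In both copies of Appendix 1, section 6.5, add the exception already used in main section 6.6: post-dose phosphate results go only to the designated unblinded investigator and are withheld from blinded staff as in 5.6. Leave the rest of the chemistry panel routed as in 6.6.
2. As a separate decision that goes beyond 5.6 and 6.6, apply the same masking to post-dose 1,25(OH)2 vitamin D and PTH, on the grounds in Appendix 1, section 1.2.
3. Reconcile these rules with Appendix 1, sections 1.4 and 7.2. They leave the handling of hypophosphatemia, and the reporting of interventions for it, to the investigator without saying whether that person is blinded. No clinical rule is proposed here; the passages need to agree on who holds the information.
4. If sub-study visits have already taken place, document who actually received the phosphate results.

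The cost is a short protocol clarification and a central-laboratory report setting. The unblinded recipient already exists under section 6.6. Item 2 adds a new masking rule, so it needs somewhat more than a clarification.
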